2.2 RATIONALE

The current treatments of senile or actinic purpura include oral arnica, and topical arnica, vitamin K, retin-A, retinol, growth factors, alpha hydroxyl acids, ceramides, and niacinamide. However, all of these have very limited results, if any, and there have been no large-scale studies proving their long-term efficacy for this condition.

If broadband light (BBL) is used to reduce photo-damage, decrease post-procedural purpura, is associated with a significantly altered expression of RNAs similar to that in youthful skin, and has been reported to increase collagen production and epidermal thickening, then it follows that this treatment may be an ideal option for reduction of senile purpura.

2.3 POTENTIAL RISKS AND BENEFITS

2.3.1 KNOWN POTENTIAL RISKS

Common potential risks of BBL include swelling, pain, scabbing, blistering, reduction of hair and lentigenes, erythema, pruritus, lightening and darkening of the skin, and reactivation of herpes infection. Rare but potential risks of BBL include severe burn, skin ulceration, scarring and infection.

Common potential risks of a skin biopsy include bleeding and scarring while rare but potential risks include infection and allergy to the lidocaine, bandages, or sutures used in the procedure.

2.3.2 KNOWN POTENTIAL BENEFITS

Improvement of the subject's ecchymoses leading to an aesthetic improvement. This aesthetic improvement may positively impact the subjects' psychological well-being. In addition, the treatment may lead to less skin tears by increasing the epidermal thickness which would prevent bleeding, infection risk, and scarring.

3 STUDY DESIGN, OBJECTIVES, AND ENDPOINTS

3.1 DESCRIPTION OF THE STUDY DESIGN

- A Prospective, Randomized, Split-Arm Clinical Study
- Single Center
- Study agent: Sciton's BBL
- Study Interventions: BBL Treatment on Day 0, Day 7, and Day 21
- Evaluations on Day 0, Day 7, Day 14, Day 21, Day 22, Day 51.

This will be a prospective, split-arm clinical study in which 5 subjects will be randomized to which arm will be treated with Sciton's BBL.

All subjects will have their arms shaved prior to the procedure and cleaned thoroughly with alcohol. After the procedure a zinc-based sunscreen will be applied to both arms.

Before each of the four treatments and 30 days after the last treatment, the subjects' number and square area of ecchymoses will be measured by an evaluator. Side effects will be measured on Day 0, 1, 2, 7, 14, 21, 22 and 51. Digital photography of subject's arms will be done on day 0, 7, 14, 21, and 51.

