I agree to ensure that all staff members involved in the conduct of this study are informed about their obligations in meeting the above commitments.

Principal Investigator: [name]

_Date: ______ Signature

Title:

A Prospective, Randomized, Split-Arm Clinical Study Investigating the Efficacy and Safety of Sciton's Broad Band for the Treatment and Prevention of Senile Purpura

Précis:

There will be ten subjects, 5 older subjects over 65 years of age with at least one ecchymotic lesion on each arm measuring at least one cm, and 5 subjects under 35 years of age. All subjects will be randomized to undergo 4 Sciton Broad Band Light (BBL) treatments on either their left or right arm one week apart. Subjects will fill out questionnaires, have pictures of their lower arms taken, and will be graded and measured by evaluators regarding the number and size of their ecchymoses as well as side effects such as blistering, pain, erythema, and swelling. One day after their 4th treatment, subjects will have biopsies done to be analyzed for changes in histology and gene expression. The subjects will follow up at 30 days after their last treatments for final pictures of their lower arms and evaluations.

Objectives:

Primary Objectives: To assess the efficacy of BBL in improving the appearance of senile purpura

Important Secondary Objectives:

- 1. To assess the safety of a new BBL protocol for treating and preventing senile purpura
- 2. To assess the efficacy of BBL in reducing skin tears
- 3. To assess the efficacy of BBL to improve the histology of the skin
- 4. To assess the efficacy of BBL to increase epidermal thickness
- 5. To assess the efficacy of BBL to change gene expression

Endpoint

Primary Endpoints:

- Mean absolute difference in the BBL treated arms as compared to the non-treated arms of those with senile purpura in the total square area of purpuric lesions from the first treatment to 30 days after the last treatment
- Mean absolute difference in the BBL treated arms as compared to the non-treated arms of those with senile purpura in the number of purpuric lesions from the first treatment to 30 days after the last treatment

Important Secondary Endpoints:

1. Measurement of pain, swelling, blistering, erythema, and all sideeffects immediately after each procedure, as well as 24 hours, 48 hours, and 7 days after the procedure.

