- 2. Mean absolute difference in the number of skin tears at baseline and 30 days after the last treatment
- 3. The changes in collagen and elastin between untreated and treated skin
- 4. Mean absolute difference in the change in epidermal thickness between treated and untreated skin
- 5. Changes in gene expression between treated and untreated skin

Population: Sample size 10

Male and female adults over the age of 21 living in Palm Beach

County Florida.

Number of Sites 1

Study Agent: Sciton's BBL

Study Duration: 51 days

SCHEMATIC OF STUDY DESIGN

Day -30 to 0 Screening

- •Total n=10
- Obtain informed consent
- Screen potential subjects by inclusion and exclusion criteria (Eligibility Questionnaire)

Day 0: Randomization

•Subjects randomized to have BBL on either their left or right

Day 0: Baseline assessments/ Study Intervention

• Baseline Assessments:

Pre-procedure pictures of patient's lower arms taken with a Digital Camera

Baseline assessment and measurement by evaluator

Baseline Medical History and Medication questionnaires completed by all subjects

• Study Intervention #1:

Sciton's BBL done according to purpura protocol on one arm according to randomized assignment

• Post-Procedure Assessments:

Post-procedure questionnaires filled out by all subjects

Day 1: Follow-up assessments

• At Home Follow-up Assessments Questionnaire Regarding Side-Effects

Day 2: Follow-up assessments

• At Home Follow-up Assessments Questionnaire Regarding Side-Effects

Day 7 +/- 2 Days: Follow-up assessments / Study Intervention

Follow-up assessments:

Evaluator assessment and measurement

Pictures taken of subject's lower arms

Subject follow up questionnaires filled out by all subjects

• Study Intervention #2:

Sciton's BBL done a second time on the assigned arm according to protocol settings

• Post-Procedure Assessments:

Day 14 +/- 2 Days: Follow-up assessments / Study Intervention

• Follow-up assessments:

Evaluator assessment and measurement Pictures taken of subject's lower arms

Subject follow up questionnaires filled out by all subjects

• Study Intervention #3:

Sciton's BBL done a third time on the assigned arm according to protocol settings

• Post-Procedure Assessments:

Post-procedure questionnaires filled out by all subjects immediately after treatment

Day 21 +/- 2 Days: Follow-up assessments / Study Intervention

• Follow-up assessments:

Evaluator assessment and measurement

Pictures taken of subject's lower arms

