3.2.3 SECONDARY ENDPOINTS

- 1. Measurement of pain, swelling, blistering, erythema, and all side-effects immediately after each procedure, as well as 24 hours, 48 hours, and 7 days after the procedure.
- 2. Mean absolute difference in the number of skin tears at baseline and 30 days after the last treatment
- 3. The changes in collagen and elastin between untreated and treated skin
- 4. Mean absolute difference in the change in epidermal thickness between treated and untreated skin
- 5. Changes in gene expression between treated and untreated skin

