6 STUDY PROCEDURES AND SCHEDULE

6.1 STUDY PROCEDURES/EVALUATIONS

6.1.1 STUDY SPECIFIC PROCEDURES

- Medical history obtained and verbally verified
- Assigned arm meeting inclusion criteria is shaved to remove all hair
- Digital Pictures taken of bilateral hands and arms
- Counseling the subjects on the treatment that they will be receiving and post-care instructions.
- The study coordinator will check before the patient leaves that all appropriate photos and paperwork have been completed.
- BBL study treatment will be done according the protocol below outlining specific settings

BBL Only Protocol

1st Treatment Settings

- 1. SkinTyte Filter ST: 150 Joules, 15msec, 15 degrees for 10 continuous passes in alternating directions (5 each direction)
- 2. 590 Filter: 8J, 15msec, 15 degrees x 2 passes
- 3. 590 Filter: 10J 15msec, 15 degrees x 2 passes
- 4. 560 Filter: 8J, 15msec, 15 degrees x 2 passes

2nd Treatment Settings

If any answers on the post procedure side effects questionnaire from day 0,1, or 2 were SEVERE or if the patient had blisters from the previous treatment

Decrease Step 3 & 4 by 2 Joules

1. SkinTyte Filter ST: 150 Joules, 15msec, 15 degrees for 10 continuous passes in alternating directions

- 2. 590 Filter: 8J, 15msec, 15 degrees x 2 passes
- 3. 590 Filter: 8J 15msec, 15 degrees x 2 passes
- 4. 560 Filter: 6J, 15msec, 15 degrees x 2 passes

If any answers on the post procedure side effects questionnaire on day 0,1, or 2 were MODERATE with NO blistering

Decrease Step 3 & 4 by 1 Joule

- 1. SkinTyte Filter ST: 150 Joules, 15msec, 15 degrees for 10 continuous passes in alternating directions
- 2. 590 Filter: 8J, 15msec, 15 degrees x 2 passes
- 3. 590 Filter: 9J 15msec, 15 degrees x 2 passes
- 4. 560 Filter: 7J, 15msec, 15 degrees x 2 passes

If all answers on the post procedure side effects questionnaire on day 0,1, or 2 protocol were MINIMAL

Keep Settings the same as previous visit

- 1. SkinTyte Filter ST: 150 Joules, 15msec, 15 degrees for 10 continuous passes in alternating directions (5 each direction)
- 2. 590 Filter: 8J, 15msec, 15 degrees x 2 passes
- 3. 590 Filter: 10J 15msec, 15 degrees x 2 passes
- 4. 560 Filter: 8J, 15msec, 15 degrees x 2 passes

If all answers on the post procedure side effects questionnaire on day 0,1, or 2 protocol were NONE

Increase Step 1 by 10 additional passes and Increase Step 3 & 4 by 1 Joule

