- 1. SkinTyte Filter ST: 150 Joules, 15msec, 15 degrees for 20 continuous passes in alternating directions (10 each direction)
- 2. 590 Filter: 8J, 15msec, 15 degrees x 2 passes
- 3. 590 Filter: 11J 15msec, 15 degrees x 2 passes
- 4. 560 Filter: 9J, 15msec, 15 degrees x 2 passes

3rd and 4th Treatment Settings

-If any answers on the post procedure side effect questionnaire were SEVERE or if the patient had blisters from the previous treatment

Decrease Step 3 & 4 by 2 Joules from settings at previous visit

-If any answers on the post procedure side effect questionnaire were MODERATE with NO blistering

Decrease Step 3 & 4 by 1 Joule from settings at previous visit

-If any answers on the post procedure side effect questionnaire were MINIMAL with NO blistering

Keep Settings the same as previous visit

-If all answers on the post procedure side effect questionnaire were NONE

Increase Step 1 by 10 additional passes and Increase Step 3 & 4 by 1 Joule from settings at previous visit

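### Secondary endpoint 1 needs 16 side-effect checks per subject but Section 3.1 lists days for only 10, leaving no 24 h or 48 h answers scheduled before treatments 3 and 4 are set

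*Combined protocol and SAP*

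**What the plan says.** The précis sets the number of treatments: "All subjects will be randomized to undergo 4 Sciton Broad Band Light (BBL) treatments", a week apart. The schematic, Sections 6.2.2 and 6.2.3 and the events table put them on nominal Days 0, 7, 14 and 21.

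Secondary endpoint 1 (Section 3.2.3, and the same in the synopsis) asks for pain, swelling, blistering, erythema and other side effects "immediately after each procedure, as well as 24 hours, 48 hours, and 7 days after the procedure".

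Section 3.1 gives the measuring days: "Side effects will be measured on Day 0, 1, 2, 7, 14, 21, 22 and 51".

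The schematic has an entry reading "At Home Follow-up Assessments Questionnaire Regarding Side-Effects" on Days 1 and 2 only. Its post-procedure entries for Days 14 and 21 read "Post-procedure questionnaires filled out by all subjects immediately after treatment". The Day 7 post-procedure entry is blank in the available text, so nothing here rests on it.

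Section 6.1.1 turns the answers into device settings. The treatment 2 rule names its days: "If any answers on the post procedure side effects questionnaire from day 0,1, or 2 were SEVERE", with parallel wording for the lower grades. The rules for treatments 3 and 4 name no days. Their escalation branch begins "If all answers on the post procedure side effect questionnaire were NONE" and then directs: "Increase Step 1 by 10 additional passes and Increase Step 3 & 4 by 1 Joule from settings at previous visit".

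**The concern.** The safety of a new BBL protocol is the first secondary objective, and these side-effect answers serve it twice: they are the endpoint data, and they determine the next dose. If the days in Section 3.1 are what the site follows, two things go wrong.

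First, the endpoint cannot be reported as defined, because most of the 48 h checks and half of the 24 h checks are never scheduled.

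Second, the settings for treatments 3 and 4 are chosen with less information than those for treatment 2, although energy and passes may by then have been raised. Section 6.1.1 states no ceiling: a subject answering NONE throughout goes from 10 J/8 J (steps 3 and 4) with 10 passes at step 1 to 13 J/11 J with 40 passes at treatment 4. A non-blistering reaction that appears and settles about 24 to 48 h after treatment 2 or 3 would reach the next decision only through recall.

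**Working it through.** The plan gives no count of its own, so this is an enumeration.

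**Inputs.** Treatment days 0, 7, 14, 21 (schematic, 6.2.2, 6.2.3, events table). Offsets 0, 1, 2 and 7 days (3.2.3). Listed days 0, 1, 2, 7, 14, 21, 22, 51 (3.1). Ten subjects (précis).

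**Required checks** = treatment day + offset: 4 × 4 = 16. A day serving two treatments counts for both; Day 7, for example, is the 7-day check for treatment 1 and the immediate check for treatment 2.

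| Treatment (day) | Immediate | 24 h | 48 h | 7 days | Listed |
|---|---|---|---|---|---|
| 1 (0) | 0 yes | 1 yes | 2 yes | 7 yes | 4/4 |
| 2 (7) | 7 yes | 8 **no** | 9 **no** | 14 yes | 2/4 |
| 3 (14) | 14 yes | 15 **no** | 16 **no** | 21 yes | 2/4 |
| 4 (21) | 21 yes | 22 yes | 23 **no** | 28 **no** | 2/4 |
| Listed | 4/4 | 2/4 | 1/4 | 3/4 | 10/16 |

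- Absent: 16 − 10 = 6, and 6/16 = 38%. For treatments 2 to 4: 6 of 12 = 50%.
- By distinct day, 7 of 13 required days are listed; the same six are absent.
- Over ten subjects: 10 × 16 = 160 required, 10 × 6 = 60 not scheduled.

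**Sensitivity.** Day 22 is credited because it is Visit 5 and Section 7.3 requires adverse-event inquiry at every visit. The events table has no adverse-effect mark for that visit and Section 6.2.4 lists no such step; on the schematic and events table alone the count is 9 of 16. The treatment bullet in 3.1 omits Day 14; taken literally, three treatments would give 8 of 12. The ±2 day windows add no checks, since each allows for one visit, and at Days 7 and 14 that visit is itself the next treatment.

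**Dose decisions.** Scheduled 24 h and 48 h answers after the preceding treatment: 2 of 2 before treatment 2, 0 of 2 before treatment 3, 0 of 2 before treatment 4.

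**Nominal recall gap at the next measuring visit.** After treatment 2: 14 − 8 = 6 and 14 − 9 = 5 days. After treatment 3: 21 − 15 = 6 and 21 − 16 = 5 days. After treatment 4: 51 − 23 = 28 and 51 − 28 = 23 days.

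**Conditional example.** A subject receives 10 J and 8 J at treatment 2, answers NONE to everything immediately, then has a MODERATE non-blistering reaction at 24 to 48 h that is not recalled.

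- Rule applied on NONE: 10 + 1 = 11 J, 8 + 1 = 9 J, and 10 extra passes.
- Rule on MODERATE: 10 − 1 = 9 J, 8 − 1 = 7 J.
- Ratios: 11/9 = 1.22 and 9/7 = 1.29, so 22% and 29% higher.

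**Related minor point.** Section 7.3 limits recorded events to onsets by Day 21 + 7 = 28 (non-serious) or Day 21 + 14 = 35 (serious). The same section also asks for every on-study event to be documented, and Section 6.2.5 records events on Day 51. The texts differ only for onsets on Days 29 to 51 (23 days, non-serious) or Days 36 to 51 (16 days, serious).

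**The case against.** The strongest reply is that the endpoint is itself an instruction to collect data after every treatment, and that Section 3.1 is a loose summary: it drops treatment 3 from its list of treatment days and mentions 5 subjects where the précis has 10. On that view the form named in the rules for treatments 3 and 4 is the same one used for treatment 2, over the same days. That may well be the intent. But nothing in the schematic, Sections 6.2.3 and 6.2.4 or the events table tells staff to issue a form on the six absent days.

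A second reply is that recall is supported. Adverse events are recorded before each later treatment (6.2.3), Section 7.3 requires inquiry since the last visit, blisters trigger a decrease without any form, and the visit questionnaire may ask for graded effects over the past week. These safeguards are real, and the content of the visit questionnaire is not in the documents. At best they give a retrospective grade 5 to 6 days later, not the answers at 24 h and 48 h that the endpoint specifies.

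Three limits stand. Only Days 8, 9, 15 and 16 can affect dosing; Days 23 and 28 concern the endpoint alone. The dose example is a constructed case whose probability cannot be derived. The recall gaps after treatment 4 are nominal, because Visit 5 may fall on Day 23 or 24. On the recording window in 7.3, the two sentences may use different terms deliberately, so that point is a request for clarification.

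**Conclusion.** The point holds. As scheduled, 10 of 16 side-effect checks per subject are covered and 6 (38%) are not. Secondary endpoint 1 could not be reported as defined, and treatments 3 and 4 would be set without the 24 h and 48 h answers that the treatment 2 rule uses.

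This rests on four treatments at nominal Days 0, 7, 14 and 21, on reading all four time points as applying to each treatment, and on crediting Day 22. The total of 60 unscheduled checks out of 160 also assumes ten subjects; the gap per subject does not. Confidence is high for the missing days. How often a dose decision would actually change is unknown and depends partly on a questionnaire that cannot be seen. The primary endpoint is not affected. This is a change the sponsor should make because it is cheap and concerns safety.

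**What to change.** - In Section 3.1, the schematic and Sections 6.2.3 and 6.2.4, schedule the existing home side-effect form at 24 h and 48 h after every treatment, counted from the actual treatment date because visits may move by 2 days either way. On Day 22 it can be completed at Visit 5 if that visit falls 24 h after treatment 4.
- Add one remote contact 7 days after treatment 4.
- In Section 6.1.1, state that the immediate, 24 h and 48 h answers after the preceding treatment feed the rules for treatments 3 and 4, as for treatment 2.
- Minor: extend the recording window in Section 7.3 to the Day 51 visit.

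**Cost.** Wording changes, plus five home forms (Days 8, 9, 15, 16, 23) and one remote contact (Day 28) per subject. For ten subjects that is 5 × 10 = 50 forms and 10 contacts, with 10 further forms on Day 22. Assuming 5 to 15 minutes per remote contact, staff time is 50 to 150 minutes in total, plus reminders and data entry. Subject burden rises slightly; no clinic visits are added. Narrowing the endpoint to the days now listed would also remove the mismatch, but given the per-subject dose adjustment, scheduling the checks is better.

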Subject follow up questionnaires filled out by all subjects

• Study Intervention #4:

Sciton's BBL done a fourth time on the assigned arm according to protocol settings

• Post-Procedure Assessments:

Post-procedure questionnaires filled out by all subjects immediately after treatment

Day 22 +/- 2 Days: Follow-up assessment via skin biopsy

• A 4mm punch biopsy will be done on both the treated and untreated arm approximately 4cm below the crease in the antecubital fossa

Day 51 +/- 2 Days: Follow-up assessment

Follow-up assessments:

Evaluator assessment and measurement

Pictures taken of subject's lower arms

Subjects follow up questionnaires filled out by all subjects

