5.1.2 DURATION OF THERAPY

- The BBL treatment will take approximately 15 minutes
- The last treatment will be done on Day 21

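### The 48-hour and 7-day side-effect checks after treatment 4 (Days 23 and 28) are required by secondary endpoint 1 but scheduled nowhere

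*Combined protocol and SAP*

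**What the plan says.** - **Objective.** The first secondary objective in the opening summary of the protocol is "To assess the safety of a new BBL protocol for treating and preventing senile purpura".
- **Endpoint.** Section 3.2.3, item 1 (repeated in the summary), measures pain, swelling, blistering, erythema and "all side-effects immediately after each procedure, as well as 24 hours, 48 hours, and 7 days after the procedure".
- **Treatment days.** The schematic, 6.2.2, 6.2.3 and 6.2.8 place the four treatments on Days 0, 7, 14 and 21, the last three with a window of 2 days either side. Section 5.1.2 on duration of therapy confirms the end: "The last treatment will be done on Day 21". The intervention bullet in 3.1 omits Day 14, but every other place includes it.
- **Collection days.** Section 3.1: "Side effects will be measured on Day 0, 1, 2, 7, 14, 21, 22 and 51".
- **At-home form.** The schematic has an entry "At Home Follow-up Assessments Questionnaire Regarding Side-Effects" under Day 1 and Day 2 and under no other day.
- **Visit 5.** The schematic describes it as "Day 22 +/- 2 Days: Follow-up assessment via skin biopsy". Neither the Visit 5 steps in 6.2.4 nor the adverse-effects row of the 6.2.8 table includes side-effect or adverse-event collection at this visit.
- **Dose rules (6.1.1).** For treatment 2 the rule names its days: "If any answers on the post procedure side effects questionnaire from day 0,1, or 2 were SEVERE". For treatments 3 and 4 it names none: "If any answers on the post procedure side effect questionnaire were SEVERE or if the patient had blisters from the previous treatment".

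**The concern.** The endpoint and the schedule do not match. At treatments 1 to 3 the next treatment visit doubles as the 7-day check. Treatment 4 has no next treatment visit, and nothing was put in its place. If the protocol is followed as written, secondary endpoint 1 cannot be measured as defined after the final treatment.

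That treatment matters most for the safety objective, because it completes the new four-treatment course. It can also carry the highest dose. Under 6.1.1, a subject who reports no side effects throughout gains 10 passes in step 1 and 1 J in steps 3 and 4 at each of three later treatments. Treatment 4 would then use 10 + 3 × 10 = 40 passes in step 1, 10 + 3 = 13 J in step 3 and 8 + 3 = 11 J in step 4. Erythema, swelling, pain or blistering present a week later may have resolved by Day 51, so severity and duration would rest on memory.

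**Working it through.** **Inputs.** Treatment days 0, 7, 14, 21 (schematic, 6.2.2, 6.2.3, 6.2.8). Required offsets 0, 1, 2 and 7 days (3.2.3). Listed days 0, 1, 2, 7, 14, 21, 22, 51 (3.1).

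**Step 1: required day = treatment day + offset, compared with the 3.1 list.**

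| Treatment | Immediate | 24 h | 48 h | 7 days | Listed |
|---|---|---|---|---|---|
| 1 (Day 0) | 0 yes | 1 yes | 2 yes | 7 yes | 4 of 4 |
| 2 (Day 7) | 7 yes | 8 no | 9 no | 14 yes | 2 of 4 |
| 3 (Day 14) | 14 yes | 15 no | 16 no | 21 yes | 2 of 4 |
| 4 (Day 21) | 21 yes | 22 yes | 23 no | 28 no | 2 of 4 |
| Listed | 4 of 4 | 2 of 4 | 1 of 4 | 3 of 4 | 10 of 16 |

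Days 7, 14 and 21 each count twice, as the 7-day check on one treatment and the immediate check on the next. That is fair, because 6.2.3 records adverse events both before and after treatment at those visits. On the same count the schematic covers 9 of 16 (no side-effect entry on Day 22). The 6.2.8 table covers 7 of 16, but it shows clinic visits only, so the at-home days would not appear in it.

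**Step 2: which of the six unlisted checks have support elsewhere.** Days 8, 9, 15 and 16 follow treatments 2 and 3. The settings for treatments 3 and 4 depend on questionnaire answers after the preceding treatment, so some form must exist there, although its days are not named. No dose decision follows treatment 4, so nothing is implied for Days 23 and 28. That leaves 6 − 4 = 2 of 16 checks (12.5%) with no support. With 10 subjects (the précis) this is 2 × 10 = 20 of 160 subject-level checks. With 5 (the number in 3.1) it is 2 × 5 = 10 of 80.

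**Step 3: can the visit windows reach them?** Treatment 4 falls on Days 19 to 23, Visit 5 on Days 20 to 24 and Visit 6 on Days 49 to 53.
- 7-day check: 19 + 7 = 26 to 23 + 7 = 30. This overlaps neither visit.
- 48-hour check: 19 + 2 = 21 to 23 + 2 = 25. Visit 5 could coincide with it, but then it no longer serves as the 24-hour check, and it lists no adverse-event step in either case.

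**Step 4: delay to the next scheduled collection after Visit 5.** Treatment 4 to Visit 6: 51 − 21 = 30 days. With windows the range is 49 − 23 = 26 to 53 − 19 = 34 days.

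**The case against.** Five points can be made for the plan.

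1. **Section 3.1 may be shorthand.** The form used on Days 0, 1 and 2 for the treatment 2 decision probably recurs after treatments 2 and 3, since the later dose rules cannot run without it. This stands. A reader might infer from the count in 3.1 that six checks, or 60 of 160 with 10 subjects, are truly absent. The documents do not support that: four of the six are unnamed rather than missing. The argument does not extend to treatment 4.
2. **Section 7.3 keeps these events in scope.** Non-serious events are recordable until 7 days after the last intervention, nominally Day 28. Each visit asks about events since the last one, severity changes are documented, and events are followed to resolution. A medical monitor reviews events regularly (7.6). So it would be wrong to say that side effects after treatment 4 go uncollected. But 7.3 schedules no contact on Day 23 or Day 28, and a question at Day 51 is recall, not measurement at 48 hours or 7 days.
3. **The coverage of treatments 1 to 3 is itself nominal.** With 2 days either side on both visits, the gap from treatment 2 to the next visit runs from 12 − 9 = 3 to 16 − 5 = 11 days, and likewise for treatment 3. This stands. The difference for treatment 4 is that no visit is intended for the purpose and no window reaches it.
4. **The evidence is incomplete.** The questionnaires are not in the file, and the post-procedure entry for Day 7 in the schematic is blank as read. The point is therefore limited to scheduled days. It rests mainly on 3.1, 6.2.4, 6.2.5 and 6.2.8, not on the schematic alone.
5. **This is one secondary endpoint in a small pilot.** The statistical section specifies no analysis for it. That limits the consequence but does not remove the mismatch.

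**Conclusion.** The mismatch is real and modest. Section 3.1 nominally lists 10 of the 16 required checks. Four of the rest are implied without days, and two, at 48 hours and 7 days after treatment 4, have no support anywhere. The Day 22 check is listed in 3.1 but left out of the Visit 5 steps and the table, although the general inquiry in 7.3 would apply at that visit.

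Two stronger readings should be avoided. A reader might infer that no 24-hour check is listed after any treatment but the first. Day 22 in 3.1 is 24 hours after treatment 4, so the correct statement is that only treatment 1 has both the 24- and 48-hour checks listed. A reader might also infer that a planned comparison of 48-hour results across treatments is lost. The plan states no such comparison, and settings change with each subject's tolerance, so it would be confounded even with complete data.

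The conclusion assumes nominal treatment days and that no further collection days are set in forms outside the file. The primary endpoints are not affected. The plan should be corrected because the safety of the full course is a stated objective and the remedy is cheap.

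**What to change.** 1. In 3.1 and the schematic, schedule the existing at-home side-effect questionnaire 24 and 48 hours after every treatment (nominal Days 1, 2, 8, 9, 15, 16, 22, 23) and 7 days after treatment 4 (nominal Day 28). State that the timing runs from the actual treatment date and that the study days are nominal.
2. Add an adverse-event recording step to Visit 5 in 6.2.4, and a mark for Visit 5 in the adverse-effects row of the 6.2.8 table. When Visit 5 falls one day after treatment 4, the 24-hour form can be completed there.

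**Cost.** Amendment wording, plus six short forms per subject (Days 8, 9, 15, 16, 23, 28), or seven if the Day 22 form cannot be done at Visit 5. That is 60 to 70 forms for 10 subjects, or 30 to 35 for 5. Four of them follow treatments 2 and 3, where the dose rules already imply a form, so only two or three per subject follow treatment 4. No new visit or instrument is needed, and the reminder routes in 4.3 (email, text or phone) could carry the forms. The downside is some added burden on subjects.
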